9. SAFETY

9.1 Safety Variables

- Vital signs
- Physical examination
- Clinical laboratory tests
- Urinalysis
- Adverse events

9.2 Laboratory Evaluations

At screening, the HIV-1 and HIV-2 tests, Syphilis – VDRL (Confirmation with FTA-ABS if needed (Syphilis)), CMV, hepatitis screen, and β -HCG serum pregnancy tests (only for women of child-bearing potential) will be performed locally at the study site. Laboratory safety tests will consist of the following:

Serum chemistry: sodium, potassium, chloride, bicarbonate, BUN, creatinine, glucose, calcium, AST/SGOT, ALT/SGPT, total bilirubin (fractionate if total >1.5 times normal), alkaline phosphatase, albumin, Coagulation studies

Hematology (CBC): hemoglobin, hematocrit, platelets, WBC, WBC differential

The Investigator will review all clinically relevant laboratory results requested in the protocol. The diagnosis associated with any clinically significant laboratory deviations should be recorded as an AE and should indicate the underlying abnormality or diagnosis (such as renal insufficiency) as opposed to the observed deviation in laboratory results (such as elevated creatinine). If there is no underlying abnormality linked to a clinically significant abnormal laboratory value, the observed deviation should be reported as the AE.

9.2.1 Pulse Oximetry

Pulse oximetry will be used to observe oxygen saturation when measuring vital signs at the infusion visit (Reference Appendix 1). Pulse oximetry will also be used throughout infusions and 2 hours following infusions. Subjects should have a resting oxygen saturation of $\geq 93\%$ prior to infusion. Subjects requiring oxygen, need the peripheral artery oxygen saturation (SaO_2) to be $\geq 93\%$ when given a maximum of 2L/minute supplemental

O_2 via nasal cannula. Infusion toxicity will be assessed based on decreases in oxygen saturation during infusion. The infusion will be stopped if the oxygen saturation does not return to >93% within 3 minutes of initiating supplemental oxygen or if the subject requires greater than 2L/min supplemental oxygen to achieve the required saturation of >93%. If this occurs, then subjects will be admitted to the hospital for observation.

9.2.2 Pregnancy

There is no information regarding allogeneic hMSCs and its effects or potential risks to a fetus or unborn child. The Principal Investigator and DSMB must be notified within twenty-four hours of investigator's awareness of the pregnancy via facsimile if a study subject becomes pregnant during the study. Any two of the enumerated contraceptive items will be acceptable for meeting the studies contraceptive requirements as listed in paragraph 2 of section 8.2.2. Females will be defined as non-childbearing potential if surgically sterilized (i.e. bilateral tubal ligation, bilateral oophorectomy, or complete hysterectomy) or post-menopausal (defined as 12 months no menses with an alternative medical cause and with a follicle stimulating hormone FSH ≥ 25.8 IU/L). Non-sterilized males who are sexually active with a female partner of childbearing potential must use any two of the acceptable forms of contraceptive items as listed below:

Acceptable forms of contraception include: 1) abstinence, 2) condoms (male or female) with a spermicidal agent, 3) diaphragm or cervical cap with spermicidal agent, 4) intrauterine device (IUD), 5) oral contraceptive, 6) injectable or transdermal hormonal contraceptive, 7) successful vasectomy with resulting azoospermia or azoospermia for any other reason, and 8) hysterectomy, bilateral oophorectomy, or tubal ligation.

Prior to study enrollment, women of childbearing potential must be advised of the importance of avoiding pregnancy during trial participation and the potential risk factors for a pregnancy. The subject must sign an informed consent and written authorization for use and disclosure of PHI document stating that the above-mentioned risk factors and the consequences were discussed with her.

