4. SUBJECT SELECTION

4.1 Inclusion Criteria

In order to participate in this study, a subject MUST:

- Be ≥ 21 and ≤ 90 years of age.
- Provide written informed consent.
- Have endothelial dysfunction defined by impaired flow-mediated vasodilation (FMD $<7\%$).
- Have DM type 2 documented by hemoglobin A1C $\geq 7\%$ or on medical therapy for diabetes.
- Females of childbearing potential must use two forms of birth control for the duration of the study. Female subjects must undergo a serum pregnancy test at screening and within 36 hours prior to infusion.

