Liver Function Tests: Albumin, alkaline phosphatase, alanine transaminase (ALT), aspartate aminotransferase (AST), and bilirubin (fractionate if total >1.5 times normal).

Renal Function Tests: creatinine, blood urea nitrogen (BUN), glomerular filtration rate, sodium, potassium, chloride, calcium, total protein, carbon dioxide and glucose.

4 - **Coagulation Tests:** prothrombin time (PT/INR), activated partial thromboplastin time (aPTT) at screening.

5 – Viral Serology testing at screening will include the following: HIV 1 and HIV 2 antibody screen, Hepatitis B (Hep B surface antigen, surface antibody, and core antibody), Hepatitis C antibody, Syphilis (VDRL or RPR, with reflex FTA-antibody if positive), and CMV antibody.

6 – For females of childbearing potential: serum pregnancy test (β HCG) will be completed at screening and within 36 hours before infusion.

7 – During immune monitoring for graft rejection, **Panel reactive antibodies (PRA)** will be performed from the serum of the subjects to check for donor specific antibodies **at Baseline and Month 3 only.**

8 – The following markers may be used for analysis to assess for activated T-cells based upon a CD3 $^+$ CD25 $^+$ (late/chronic T cell activation) or CD3 $^+$ CD69 $^+$ phenotype (early T cell activation).

9 – The following biomarkers may be analyzed at any or all of the time points in Table 1:

Circulating pro-inflammatory markers: serum high sensitivity C-reactive protein (hs-CRP), IL-6, IL-1, and TNF α

Circulating angiogenic factors known to mobilize and recruit EPCs: VEGF, SDF-1 α , and SCF

Transcriptomic/Proteome: DNA (at baseline only), RNA (**at Baseline and Month 3 only**)

10 – Endothelial Progenitor Cell-Colony Forming Units (EPC-CFUs): Blood will be collected in Lavender top tubes (EDTA) for EPC-CFU analysis.

11 - Postdoctoral (experimental laboratory) studies:

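### The post-menopausal definition in Section 9.2.2 contradicts itself and, read literally, swaps two groups of women under the contraception rule

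*Combined protocol and SAP*

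**What the plan says.** Section 9.2.2 gives two routes to non-childbearing potential. The first is surgical: "Females will be defined as non-childbearing potential if surgically sterilized". The second is to be "post-menopausal (defined as 12 months no menses with an alternative medical cause and with a follicle stimulating hormone FSH" at or above a cut-off, given as "follicle stimulating hormone FSH ≥ 25.8 IU/L". No other section restates or corrects this definition.

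Several rules depend on the class:

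- Section 4.1, and the same bullet in the synopsis: "Females of childbearing potential must use two forms of birth control for the duration of the study".
- Section 4.2 and the synopsis exclude women of childbearing potential who are not using effective contraception.
- Table 1 key, item 6: "For females of childbearing potential: serum pregnancy test", which "will be completed at screening and within 36 hours before infusion".
- Section 9.2: "serum pregnancy tests (only for women of child-bearing potential) will be performed locally at the study site".

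On testing, one sentence points the other way. Directly after the contraception sentence, the bullet in Section 4.1 and the synopsis requires the serum pregnancy test of female subjects, without limiting it to those of childbearing potential.

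FSH appears in the Section 9.2.2 definition. It is not in Table 1, the Table 1 key or the laboratory list in Section 9.2.

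**The concern.** If the absence of menses has an alternative cause, menopause is not the explanation. The clause makes such a cause a condition for being called post-menopausal, so a woman in natural menopause, who has none, cannot meet it. The contradiction is visible from the sentence itself, which is complete and grammatical, so it does not look like an artefact of text extraction.

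This is an operative eligibility rule, not background text. A site that follows the words would release from the two-method rule a woman whose amenorrhoea is explained by some other condition. It would hold a naturally post-menopausal woman to that rule, and exclude her if she does not practise contraception. Eligible ages run from 21 to 90, so women on both sides of menopause can be screened. Section 9.2.2 also states that nothing is known about the product's effect on a fetus, and Section 9.9 requires any subject who becomes pregnant to be withdrawn. In a trial of 16 subjects, a single wrong exclusion or avoidable withdrawal would be noticeable.

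**Working it through.** The plan states no figure on this point and no sample-size or error-rate calculation applies. The check is logical.

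**Inputs**, all from Section 9.2.2, for a woman who is not surgically sterilised:

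- A: 12 months of no menses.
- B: an alternative medical cause is present.
- C: FSH at or above 25.8 IU/L.

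**Rules compared.** As written, non-childbearing = A and B and C. The opposite reading, in which another cause disqualifies, is non-childbearing = A and not-B and C. Three yes/no conditions give 2 × 2 × 2 = 8 combinations.

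| A | B | C | As written | Opposite reading |
|---|---|---|---|---|
| yes | yes | yes | non-childbearing | childbearing |
| yes | no | yes | childbearing | non-childbearing |
| yes | yes | no | childbearing | childbearing |
| yes | no | no | childbearing | childbearing |
| no | yes | yes | childbearing | childbearing |
| no | no | yes | childbearing | childbearing |
| no | yes | no | childbearing | childbearing |
| no | no | no | childbearing | childbearing |

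The readings differ in 2 of 8 rows and agree in 8 − 2 = 6. Both differing rows have A and C true, and in both the class flips.

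**What each flipped row means under the text as written:**

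| Rule | No menses, FSH at or above cut-off, another cause | No menses, FSH at or above cut-off, no other cause |
|---|---|---|
| Two methods (4.1, synopsis) | exempt | required |
| Exclusion without contraception (4.2, synopsis) | does not apply | applies |
| Pregnancy test per Table 1 key item 6 and 9.2 | not required | required |
| Pregnancy test per second sentence of the 4.1 bullet and synopsis | required, if read as covering all women | required |

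The first two rules give a definite consequence. For testing, the first group is exempt under Table 1 and Section 9.2 but can be read as tested under Section 4.1. The documents do not settle which governs.

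**FSH.** Condition C needs a value. No scheduled assessment supplies one, and no text says whether a value from existing records is acceptable.

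**The case against.** The strongest reply is that this is a one-word drafting slip with narrow reach, and that experienced staff would see what was meant. Much of the argument about reach is right:

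- Surgical sterilisation is a separate route and is untouched.
- The FSH condition still applies, so the women wrongly exempted must have 12 months of no menses, another cause and a high FSH together. The documents say nothing about how often such amenorrhoea is reversible.
- The accepted methods in Section 9.2.2 include abstinence and a successful vasectomy. This eases the burden on naturally post-menopausal women, although two items would still formally be needed.

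A reader might go further and infer that a misclassified woman gets no pregnancy test at all. The documents do not support this as a flat statement: the Section 4.1 sentence on testing can be read as covering every female subject.

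A reader might also infer that the definition cannot be applied because FSH is not scheduled. That is too strong as well. Table 1 key item 3 describes its list as the minimum, so further tests are not barred, and the value could come from existing records. What remains is an unspecified source.

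The argument that sites will know what was meant does not stand. Following the words misclassifies women; silently correcting them is an undocumented departure from an eligibility rule.

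**Conclusion.** The point holds in a limited form. The post-menopausal limb of the only definition of non-childbearing potential contradicts the term it defines. Taken literally, it exchanges the classes of two groups: non-sterilised women with 12 months of no menses and FSH at or above 25.8 IU/L, with and without another cause. The effects on the contraception rule and on the Section 4.2 exclusion follow directly. The effect on pregnancy testing is unresolved because Sections 4.1, 7.1 and 9.2 do not agree; that inconsistency needs settling in its own right.

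It would be going too far to say that the protocol's whole classification is reversed, since 6 of the 8 combinations and the surgical route are unaffected. The number of women concerned cannot be given: the documents do not state the expected sex or age mix of the 16 subjects. The conclusion assumes only the ordinary meaning of an alternative cause, that is, one other than menopause. Sample size, significance level and analysis are unaffected. The correction should be made because the rule governs eligibility and the change costs very little.

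**What to change.** The sponsor should:

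1. Correct the clause in Section 9.2.2 so that it agrees with the term it defines. The clinical content of the definition is for the sponsor to settle.
2. Reconcile it with the synopsis criteria, Sections 4.1 and 4.2, Table 1 key item 6 and Section 9.2, and state in one place which women are pregnancy-tested.
3. Refer to the reconciled definition from Section 4.1, where sites apply it.
4. State where the FSH value comes from.

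The contraception sentence in Section 9.2.2 also points to a Section 8.2.2, which does not exist in the current numbering (8.2 is the Baseline Visit); the same edit can correct it.

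The cost is a wording correction and a cross-reference. Nothing in the sample size or the analysis changes.

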9.2.3 Determination of Infusional Toxicity

Infusional toxicity will be evaluated by continuously monitoring the subject's vital signs and O_2 saturation by pulse oximetry from the time of allogeneic hMSCs administration until two hours after infusion is complete. Since there is no specific or antidotal therapy for AEs arising from allogeneic hMSCs, any toxicity that may arise during a subject's participation in this study should be managed with supportive measures at the discretion of the treating physician.

9.2.4 Subject Stopping Guidelines

This guideline is to be used to indicate boundaries requiring discussion by the Data and Safety Monitoring Board (DSMB) and is designed to assist the independent DSMB in

overseeing the study. The DSMB may also request additional interim analyses and develop other criteria including provision for monitoring of potential late effects to determine when to intervene in the enrollment or treatment of subjects in the study.

The first more conservative stopping guideline is to monitor subjects for unexpected SAEs where there is a reasonable possibility that the study product or administration procedure caused the event within 30 days of administration including cardiorespiratory distress during infusion, subject death, myocardial infarction, hemodynamically unstable ventricular tachycardia, stroke, or more than two related, \geq Grade 3 AEs (based on the NIH CTCAEv4). Study accrual and further treatment of subjects will be put on hold (temporary suspension of study drug administration, pending a safety investigation) if any subjects experience one of these events. The DSMB will be notified within 24 hours of the occurrence of these events and will be convened within 3 business days to review the event and study.

The following are subject stopping guidelines:

- Any subject who develops persistent (that is, still existing more than 3 hours after the end of IP infusion) cardiorespiratory signs or symptoms (for example, shortness of breath, tachypnea, tachycardia, hypotension, or palpitations) will continue with all scheduled follow-up if such follow-up is considered safe in the opinion of the Investigator.
- Any subject whose infusion is stopped due to cardiorespiratory distress will receive no further IP infusions but will continue with all scheduled follow-up if such follow-up is considered safe in the opinion of the Investigator.
- Any subject who develops any sign or symptom that, at the discretion of the Investigator, warrants the discontinuation of infusion will receive no further IP infusions but will continue with all scheduled follow-up if such follow-up is considered safe in the opinion of the Investigator.
- Infusion of the IP may be stopped if there is an adverse event that the Investigator believes is related to the IP or if there is an issue with the IP infusion.
- The proportion of subjects experiencing TE-SAE as defined in Section 2.2.1 will be monitored within 30 days of injection. This guideline is designed to assist the independent DSMB in overseeing the study and indicate boundaries needing discussion by the DSMB. The DSMB may also request additional interim analyses and develop other criteria including provision for monitoring of potential late effects to determine when to intervene in the enrollment or treatment of subjects in the study.
- The stopping guidelines serve as a mechanism for consultation with the DSMB for additional review, and are not formal “stopping rules” that would mandate automatic closure of study enrollment. It is designed to assist the independent

DSMB in overseeing the study. The DSMB may also request additional interim analyses and develop other criteria including provision for monitoring of potential late effects to determine when to intervene in the enrollment or treatment of subjects in the study.

9.2.5 Subject observation and discontinuation after IP administration

The IP administration guidelines in **Appendix 1** list the study requirements for subject observation and discharge after IP administration.

9.3 Definition of an Adverse Event

An Adverse Event (AE) is any untoward medical occurrence in a subject or clinical investigation subject temporally associated with the use of a medicinal product, whether or not considered related to the medicinal product. The occurrence does not necessarily have to have a causal relationship to the treatment received in the study. An AE can therefore be any unfavorable and unintended sign (including an abnormal laboratory finding, for example), symptom, or disease (new or exacerbated) temporally associated with the use of a medicinal product, whether or not considered related to the medicinal product.

Examples of an AE include:

- Exacerbation of a chronic or intermittent pre-existing condition including either an increase in frequency or intensity of the condition.
- Significant or unexpected worsening or exacerbation of the condition/indication under study.
- A new condition detected or diagnosed after study therapy administration even though it may have been present prior to the start of the study.
- Pre- or post-treatment events that occur as a result of protocol-mandated procedures (e.g., invasive protocol-defined procedures, modification of a subject's previous treatment regimen).

An AE does **not** include:

- Medical or surgical procedures (e.g., colonoscopy, biopsy). The medical condition that leads to the procedure is an AE.
- Social or convenience hospital admissions where an untoward medical occurrence did not occur.
- Day to day fluctuations of pre-existing disease or conditions present or detected at the start of the study that do not worsen.

- The disease/disorder being studied or expected progression, signs, or symptoms of the disease/disorder being studied unless more severe than expected for the subject's condition.

9.4 Definition of Adverse Reaction

An adverse reaction is any adverse event caused by a drug. Adverse reactions are a subset of all suspected adverse reactions, for which there is reason to conclude that the drug caused the event.

9.5 Definition of Suspected Adverse Reaction

Suspected adverse reaction means any adverse event for which there is a reasonable possibility that the drug caused the adverse event. For the purposes of IND safety reporting, 'reasonable possibility' means there is evidence to suggest a causal relationship between the drug and the adverse event. A suspected adverse reaction implies a lesser degree of certainty about causality than adverse reaction, which means any adverse event caused by a drug.

9.6 Definition of Serious

An adverse event (AE) or suspected adverse reaction is considered "serious" if it:

1. results in death
2. is life-threatening (at risk of death at the time of the event)
3. requires inpatient hospitalization or prolongation of existing hospitalization

NOTE: Complications that occur during hospitalization are AEs. If a complication prolongs hospitalization or fulfills any other serious criteria, the event is serious. Hospitalization for elective treatment of a pre-existing condition that did not worsen from baseline is not considered to be an AE.

4. results in disability/incapacity

NOTE: *The term disability means a substantial disruption of a person's ability to conduct normal life functions. This definition is not intended to include experiences of relatively minor medical significance such as uncomplicated headache, nausea, vomiting, diarrhea, influenza, accidental trauma (i.e., sprained ankle) that may interfere or prevent everyday life functions but do not constitute a substantial disruption.*

5. Is a congenital anomaly/birth defect.

Important medical events that may not result in death, be life-threatening, or require hospitalization may be considered an SAE when, based upon appropriate medical judgment, they may jeopardize the subject and may require medical or surgical intervention to prevent one of the outcomes listed in the above definition.

9.7 Definition of Unexpected

An adverse event or suspected adverse reaction is considered “unexpected” if it is not listed in the investigator brochure or is not listed at the specificity or severity that has been observed; or, if an investigator brochure is not required or available, is not consistent with the risk information described in the general investigational plan or elsewhere in the current application.

9.8 Clinical Laboratory Assessments and Other Abnormal Assessments as Adverse Events and Serious Adverse Events

Abnormal laboratory findings (e.g. clinical chemistry, hematology) or other abnormal assessments (e.g., vital signs) that are judged by the Investigator as clinically significant will be recorded as AEs or SAEs if they meet the definition of an AE as defined in Section 8.3 (“Definition of an Adverse Event”) or SAE, as defined in Section 8.6 (“Definition of a Serious Adverse Event”) and will assess intensity based on the criteria defined in Section 8.10. Clinically significant abnormal laboratory findings or other abnormal assessments that are detected during the study or are present at screening and significantly worsen following the start of the study will be reported as AEs or SAEs. However, clinically significant abnormal laboratory findings or other abnormal assessments that are associated with the disease being studied, unless judged by the Investigator as more severe than expected for the subject’s condition, or that are present or detected at the start of the study but do not worsen, will not be reported as AEs or SAEs.

The Investigator will use the normal laboratory ranges (or a change in baseline in subject’s whose laboratory tests were outside of the normal range when enrolled), as well as the NIH CTCAEv4 when exercising medical judgment in assessing whether abnormal laboratory values are clinically significant.

